2. CLINICAL STUDY BACKGROUND

2.1 Piroxicam Plus Counterirritant gel

In 1972, an innovator topical analgesic product was introduced to the Indonesian market. Counterpain® is one of the topical analgesic products that is known not only in Indonesia, but also in other Southeast Asian countries such as Malaysia, Philippines, and Thailand. Counterpain® as an innovator product in Indonesia has several variants, namely Counterpain® cream helps with a warm sensation that relieve muscle pain, Counterpain® Cool with a cool sensation can be used for cooling during exercise and Counterpain® PXM effectively relieves inflammation in musculoskeletal and joint.

There are many topical preparations containing non-steroidal anti-inflammatory drugs, namely diclofenac, ketoprofen and also piroxicam. Piroxicam preparations that are registered as innovator products in Indonesia :

- Feldene® gel which only contains Piroxicam as an active substance and
- Counterpain® PXM which contains Piroxicam, and Counterirritant: methyl salicylate, menthol and eugenol as active substances.

Counterpain® PXM was first registered and obtained marketing authorization in Indonesia in 2004 by Bristol Myers Squibb (BMS). The registration process was completed by providing research data of Counterpain PXM-Thailand clinical study in 1995 as supporting data.

The pharmacokinetic parameters of piroxicam 0.5% topical gel were taken from data were determined in 20 healthy volunteers (6 women and 14 men) following application of multiple doses (20 mg piroxicam daily) over 14 days. 21 blood samples were drawn from each patient beginning just before application of the first dose, with the final sample taken 14 days after application of the last dose. Plasma concentrations of piroxicam were determined by high-performance liquid chromatography using UV detection at 340nm. There was considerable interindividual variation in piroxicam half-lives with a mean of 79 hours. Mean piroxicam plasma concentrations at steady-state were between 300 and 400 ng/ml, which is about 5% of those observed after equivalent doses of oral or intramuscular piroxicam. No adverse experiences were reported during the study period. Thus, the results of this study confirm the minimal systemic absorption of piroxicam during multiple-dose application of the 0.5% topical gel and the excellent tolerability of this mode of piroxicam therapy.

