7.7.2 Study period and process

The study period for each participant is defined as “the period from the day of consent to the end of study (the day on which final tests and observation are finished or the day of discontinuation of the study).

The participants considered as a complete visit after the 3rd visit examination on 6 ± 1 days visit.

[figure not shown]
- 1st visit consider as Day 0
- 2nd visit is on Day 3 ± 1 days
- 3rd visit is on Day 6 ± 1 days

The study's flow in Day 0 :

- 1) The registration officers will receive participants who register at the Eminence clinic and ask about symptoms related to the participant's visit. If the Participant complains of pain, the patient will be asked to fill out a registration form.
- 2) The Principal Investigator or Sub Investigator will ask some questions (anamnesis) about the symptoms and explain about a clinical study that is conducted in the clinic. The PI or Sub-I will ask the Participant's willingness to join the research and explain regarding informed consent. If the Participant agrees, an informed consent will be signed.
- 3) The participants are asked to complete the Individual Assesment of Pain.
 - a. Form 2 : Pemeriksaan Inventerisasi Rasa Nyeri Singkat
- 4) The examination was carried out by conducting anamnesis, physical examination to confirmation the musculoskeletal pain, range of motion and muscle test and confirmation related to the inclusion and exclusion criteria. If needed a radiologic examination will be conducted.
- 5) In the examination, the PI or Sub-I should complete some Forms :
 - a. Form 3 : Pemeriksaan Awal Rasa Nyeri
 - b. Form 4 : Pemeriksaan Indikator Rasa Nyeri Non Verbal
 - c. Form 5 : Pemeriksaan Rentang Gerak
 - d. Form 6 : Pemeriksaan Kekuatan Otot
- 6) The PI or Sub-I will provide a diagnosis and therapy appropriate to the diagnosis.

- 7) Randomization of participants is carried out helped by Study Coordinator. The administration of therapeutic drugs according to the randomization list by a physiotherapist. The physiotherapist will provide information related to how to apply topical drugs to participants and provide the first dose of the investigational product in the therapy room.
 - a. Form 7: Pemberian aplikasi obat topikal by Physiotherapist
 - b. Form 8: Sensasi Termal by Participant
- 8) Each participant will get physical therapy program referred to standard protocol and diagnosis

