- 2) The participant will do the re-registration to registration officer and send back the pouch that will be given to the Fisiotherapist.
- 3) The examinations will remains same as Day 0 from poin 2 until 5.
- 4) The PI or Sub-I will give information that this is the last day of the study and the investigational drugs application last dose will be given by the physiotherapist.
- 5) The administration of therapeutic drugs according to the randomization list by a physiotherapist. The physiotherapist will provide information related to how to apply topical drugs to participants and provide the last dose of the investigational product in the therapy room.
 - Form 7: Pemberian aplikasi obat topikal by Physiotherapist
 - Form 8: Sensasi Termal by Participan
- 6) End of Study.

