7.9 STUDY, EFFICACY AND SAFETY ENDPOINTS SCHEDULE

Days	1st Visit Day 0	Day 1 - Day 2	2nd Visit Day 3 ± 1 day	Day 4 - Day 5	3rd Visit Day 6 ± 1 day	Data Input & Locked Day 7 - Day 15	Note
Informed consent	X						PI, Subject
Inclusion and Exclusion Criteria	X						PI, Sub I
Medical Examination	X		X		X		PI, Sub I
Randomization	X						Study Coordinator
Dispense Study Drugs	X						PI, Sub I, Study Coordinator , Physiotherapist
Recovery Treatment : - Application of Study Drugs to affected site - Physiotherapy and exercise based on diagnosis and treatment from PI, Sub-I	X		X		X		PI, Sub PI, Study Coordinator, Physiotherapist
Primary and Secondary endpoint assessment	X		X		X		PI, Sub-I, Physiotherapist
Application of Study Drugs at home		X		X			Subject
Subject's diary	X	X	X	X	X		Subject
Concomitant medication	X	X	X	X	X		PI, Sub PI, Subject
Rescue medication	X	X	X	X	X		PI, Sub PI, Subject
Adverse events	X	X	X	X	X		PI, Sub PI, Subject
Study drugs and Diary returned					X		Registration officer, Physiotherapist
Data input	X		X		X	X	Study Coordinator
Data locked						X	Study Coordinator
Monitoring			X		X	X	CRA

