7.4.2 Statistical Analysis Plan

The statistical analysis will be performed after data finalization and database lock, following the predefined analysis sets (PPS, FAS, and Safety Analysis Set). All analyses will be conducted using standard statistical software (e.g., SPSS, SAS, or R), with the level of statistical significance set at $p < 0.05$, unless otherwise adjusted.

Efficacy Analysis

- **Primary Endpoint (Pain Score using Brief Pain Inventory):**
 - **Test: Analysis of Covariance (ANCOVA)** adjusting for baseline BPI score

- **Equivalence testing:** Pairwise comparisons using **two one-sided t-tests (TOST)** to assess whether the difference in mean change from baseline falls within the equivalence margin (± 1.0)
- **Assumptions:** Normality and homogeneity of variance will be checked. If violated, non-parametric equivalent (e.g., **Wilcoxon rank-sum test**) will be used.
- **Secondary Endpoints:**
 - **Range of Motion (ROM) and Muscle Strength:**
 - **Test:** Repeated Measures ANOVA or mixed-effects model, depending on data completeness and correlation structure
 - If non-normal: **Friedman test** or **Wilcoxon signed-rank test** for within-group, **Kruskal-Wallis test** for between-group comparisons.
 - **Thermal Sensation, Comfort, and Acceptance (ASHRAE Scale):**
 - **Test:** Chi-square test or Fisher's exact test for categorical comparisons
 - **Ordinal regression** may be used to explore patterns of thermal perception across groups.
 - **Responding Analysis (pain reduction ≥ 3 points):**
 - **Test:** Chi-square test for group-wise comparison of response rates
 - **Risk difference** and **number needed to treat (NNT)** will be calculated.

Safety Analysis

- **Adverse Events (AEs) and Adverse Drug Reactions (ADRs):**
 - **Test:** Chi-square test or Fisher's exact test for comparing incidence across groups
 - Descriptive statistics for type, severity, onset, and duration
 - **Severity grading** and **causality assessment** using **Naranjo's algorithm**.
- **Rescue Medication Use:**
 - **Test:** Poisson regression or negative binomial regression if data are overdispersed
 - Summarized as a mean number of doses used per participant and compared between groups.

Demographic and Baseline Characteristics

- **Continuous Variables** (e.g., age, BMI):
 - **Test:** One-way ANOVA or **Kruskal-Wallis test** (if non-normal distribution)
- **Categorical Variables** (e.g., sex, diagnosis):
 - **Test:** Chi-square test or Fisher's exact test as appropriate

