7.18 COMPENSATION FOR HEALTH HAZARDS

- 1) When any health hazard occurs to a subject in this study, the study site and the sponsor respond to it for the subject or his or her bereaved family in the following manner.
- 2) The study site makes all possible efforts to treat the health hazard.
- 3) If neither intention nor negligence of the sponsor was involved and no other parties have liability for the health hazard caused by the study, the sponsor provides compensation based on its compensation system. However, if the health hazard was proven to be the results of the subject's own intention or significant negligence, the compensation is reduced or not provided. If a health hazard that newly occurred is causally unrelated to the study, it is not compensated.
- 4) If intention or negligence of the sponsor, the study site, a party commissioned by the sponsor or the study site to carry out study-related tasks, or other parties was involved in the health hazard caused by the study, the party that is legally responsible for this health hazard provides the compensation.
- 5) Adverse event that happened during observation and treatment period will be monitored by investigator and sponsor. The cost for the adverse event related to the study will be compensated by sponsor.

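### For completers, adverse-event collection closes at the visit where the last dose is applied, so later reactions are not captured and open events are not followed to outcome

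*Protocol*

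**What the plan says.** The third visit is set for Day 6 ± 1. Its flow in Protocol 7.7.2 runs in this order:

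- The participant re-registers and returns the pouch, which holds the diary.
- The examinations are repeated.
- Then "The PI or Sub-I will give information that this is the last day of the study".
- The physiotherapist is to "provide the last dose of the investigational product in the therapy room", with the drug-application form and the thermal-sensation form completed.
- The study ends.

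For each participant the study period runs from consent to "the day on which final tests and observation are finished or the day of discontinuation of the study" (7.7.2). Section 7.9.2 has participants record adverse events in the diary from Day 0 until completion. In section 5.2 the investigator reviews the diary at the second and last visits. In the 7.9 schedule the adverse-event row is marked through the third visit. It is blank in the column headed "Data Input & Locked Day 7 - Day 15", where only data input, lock and monitoring are marked.

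The safety analysis in 7.4.2 compares incidence between groups and adds "Descriptive statistics for type, severity, onset, and duration". Section 7.7.3 makes the principal investigator responsible for medical care of study-related adverse events during participation and afterwards.

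**The concern.** Section 4 sets out to show equivalence of safety as well as efficacy, and adverse events are the first secondary endpoint in 5.2. The plan nevertheless stops looking at the moment of the final application. A skin reaction that evening or the next day would have no form, diary or contact to enter.

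A second gap concerns events still open at the last visit. Their duration is to be described, but no step obtains an end date or an outcome. Care after participation is promised in 7.7.3, yet nobody is assigned to record what that care finds.

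The discontinuation rules add an oddity. Under 7.8.2, a participant who stops attending may be contacted later about adverse events, with the result entered in the case report form. A participant who completes the study as planned is not contacted.

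**Working it through.** The plan states no figure for post-dose follow-up, so the check sets the sections side by side and then does simple day arithmetic.

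**What each section fixes**

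| Protocol section | What it fixes | Consequence |
|---|---|---|
| 7.7.2, third-visit flow | Diary returned, then last dose, then end | The diary is out of the participant's hands before the last application |
| 7.7.2, form after the dose | Thermal-sensation form only | Immediate sensation and comfort are recorded, later reactions are not |
| 7.9, schedule | Adverse-event row blank after the third visit | No contact in Day 7 to 15 |
| 7.9.2 | Diary recording ends with completion | For a completer, this is the third visit |
| 7.8.2 | Final observations at discontinuation; phone or letter only if these cannot be done | An early stopper who attends the final tests has no later contact |
| 7.7.3 | Care continues after participation | Care, with no recording step |
| 7.4.2 | Duration of events described | Unknown for events open at the last visit |

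**Observation after the last dose, completers**

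Observation = day of last planned adverse-event contact − day of last dose. Across the visit window this is 5 − 5, 6 − 6 or 7 − 7, which is 0 days each time. One step in 7.7.2 asks for the return visit on Day 8 ± 1 instead. The result is still 0, because contact and last dose fall on the same visit.

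**How many participants**

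Section 6.7 plans 180 participants with 10% dropout. Completers: 180 × (1 − 0.10) = 162. Early stoppers: 180 − 162 = 18.

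**What a contact in the existing window would give**

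- On Day 7: 7 − 7 = 0 to 7 − 5 = 2 days after the last dose.
- On Day 15: 15 − 7 = 8 to 15 − 5 = 10 days after the last dose.
- On Day 15 with the Day 8 ± 1 visit: 15 − 9 = 6 to 15 − 7 = 8 days.

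A contact at the start of the window would add almost nothing for a participant seen on Day 7, so it belongs late in the window.

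**What cannot be computed**

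The documents give no rate of reactions beginning after treatment ends, for any of the three products. The number of missed events cannot be estimated from them.

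**The case against.** The best case for the plan is that little exposure goes unobserved. Three applications a day over 5 to 7 days is about 15 to 21 applications, made under a daily diary and coordinator reminders. Most reactions that need several days to appear would fall inside that time. The products are used according to nationally approved leaflets (6.8.1 to 6.8.3), and the piroxicam study cited in 2.1 reported no adverse experiences. This stands as a reason to expect few missed events. It does not close the gap, because the last application and everything after it remain unobserved.

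Several stronger readings are tempting, and the documents do not support them:

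- **Late systemic reactions are likely.** Section 2.1 says: "There was considerable interindividual variation in piroxicam half-lives with a mean of 79 hours". The same section says that "the results of this study confirm the minimal systemic absorption of piroxicam during multiple-dose application", with plasma levels about 5% of those after oral or intramuscular dosing. Plasma half-life also does not measure a local skin reaction. The gap stands without this figure.
- **The piroxicam arms would look safer.** All arms share one window, no half-life or late-reaction rate is given for diclofenac, and one of the planned comparisons has piroxicam on both sides.
- **Ongoing events are not counted.** They are. An event present at the third visit enters the incidence comparison. Only its outcome and full duration may be lost.
- **Early stoppers leave with no follow-up.** Section 7.8.2 requires the scheduled observations at discontinuation, and remote follow-up when these cannot be done.
- **Section 7.18 caps monitoring.** It says: "Adverse event that happened during observation and treatment period will be monitored by investigator and sponsor". This compensation clause limits when an event occurs, not how long it is followed.

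**Conclusion.** The point holds as a limited gap in safety collection. For completers, about 162 participants under the protocol's own dropout allowance, planned adverse-event observation after the last dose is 0 days. Reactions that start after the third visit are not captured. Events open at that visit count towards incidence but have no stated follow-up to outcome, which sits badly with the planned description of duration. For early stoppers, later contact is conditional.

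The primary endpoint is untouched, and neither a direction of bias nor a number of lost events can be claimed. The conclusion rests on reading completion in 7.9.2 as the third visit, which the flow and the schedule both support. It is not a detail left to an analysis plan: the protocol itself fixes the collection period, and an analysis plan cannot recover data that were not collected.

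**What to change.** Amend the protocol in three places:

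- **7.7.2 and 7.9:** add one adverse-event telephone contact by the study coordinator for every completer, late in the existing Day 7 to 15 window, and mark the adverse-event row in that column. State that adverse-event recording in 7.9.2 runs to this contact.
- **7.8.2:** give the same contact to every early stopper, whether or not the final observations were done.
- **At the contact:** ask about events that began after the last visit, and record the outcome and end date, or still-ongoing status, of events that were open then. Lock the participant's data only after this contact.

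Use one fixed set of questions for all arms, because 6.12 has the coordinator match participants to treatment groups.

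The cost is about 180 short calls (60 per arm), one schedule entry and a slightly later lock per participant. The coordinator already gives daily reminders, and 7.8.2 already accepts follow-up by telephone. No dose or treatment rule changes.

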7.7.3 Ensuring Safety of Participants

Basic Points

- 1) The Principal Investigator is responsible for all the medical decisions related to the study.
- 2) The Principal Investigator ensures that sufficient medical care for all the AEs related to the study is provided to participants during their participation in the study and after that.
- 3) The sponsor is responsible for continuously assessing the safety of study drugs.
- 4) The sponsor promptly notifies all Principal Investigators involved in the study of the information that may adversely affect the safety of participants, influence the conduct of the study, or require changes in the approval of the continuation of the study by the institutional review board (IRB)/EC.

7.8 CRITERIA AND PROCEDURE FOR DISCONTINUATION FOR PARTICIPANTS

7.8.1 Discontinuation Criteria

Investigator discontinues the study when a subject meets the following criteria.

1. When continuation of the study is difficult due to worsening of the target disease of this study or symptoms caused by the target disease
2. When a significant or persisting noncompliance with the protocol that makes it difficult to ensure safety or influences efficacy assessment was detected

3. When a subject is found not to meet the inclusion criteria for participants of this study or to meet the exclusion criteria
4. When it is difficult to continue the study or a subject requests for discontinuation due to onset of AEs
5. When a subject requests for discontinuation (not in relation to AEs)
6. When a subject stops visiting the site, making it difficult to continue the study
7. Other cases in which Investigator considers it difficult to continue the study

7.8.2 Discontinuation Procedures

When any event corresponding to “Discontinuation Criteria” occurs during the study treatment, Investigator discontinues the administration of study drugs, performs the observation and tests specified in “ Schedule and Efficacy and Safety Endpoints,” and enter the results, discontinuation day, and reason for discontinuation in case report form.

Appropriate treatment including alternative therapies is provided after discontinuation.

When the study is discontinued due to occurrence of a safety problem in the subject concerned, appropriate measures are taken and the problem is addressed in accordance with “ Ensuring Safety of Participants.”

When a subject stops visiting the site, Investigator asks a subject to visit the site and efforts are made to perform the observation and tests specified in “Schedule, Efficacy and Safety Endpoints.”

If the designated observation and tests cannot be performed, Investigator promptly conducts follow-up investigation on the course after the latest observation and AEs over the phone, by letter, or other possible methods and enters the result in case report form. When confirmation was made with a person other than the subject for a compelling reason, the reason and the relationship of this person with the subject are entered in case report form.

7.9 STUDY, EFFICACY AND SAFETY ENDPOINTS SCHEDULE

Days	1st Visit Day 0	Day 1 - Day 2	2nd Visit Day 3 ± 1 day	Day 4 - Day 5	3rd Visit Day 6 ± 1 day	Data Input & Locked Day 7 - Day 15	Note
Informed consent	X						PI, Subject
Inclusion and Exclusion Criteria	X						PI, Sub I
Medical Examination	X		X		X		PI, Sub I
Randomization	X						Study Coordinator
Dispense Study Drugs	X						PI, Sub I, Study Coordinator , Physiotherapist
Recovery Treatment : - Application of Study Drugs to affected site - Physiotherapy and exercise based on diagnosis and treatment from PI, Sub-I	X		X		X		PI, Sub PI, Study Coordinator, Physiotherapist
Primary and Secondary endpoint assessment	X		X		X		PI, Sub-I, Physiotherapist
Application of Study Drugs at home		X		X			Subject
Subject's diary	X	X	X	X	X		Subject
Concomitant medication	X	X	X	X	X		PI, Sub PI, Subject
Rescue medication	X	X	X	X	X		PI, Sub PI, Subject
Adverse events	X	X	X	X	X		PI, Sub PI, Subject
Study drugs and Diary returned					X		Registration officer, Physiotherapist
Data input	X		X		X	X	Study Coordinator
Data locked						X	Study Coordinator
Monitoring			X		X	X	CRA

7.9.1 Primary Endpoint

The assessment of primary endpoint will be assessed through form 2, Inventerisasi Rasa Nyeri Singkat on 1st Visit, 2nd Visit and 3rd Visit.

The primary end-point is the difference BPI scale ≥ 3 , from initial scale of pain to the end of treatment will be captured as the primary efficacy endpoint.

7.9.2 Secondary Endpoint

The assessment of secondary endpoints will be assessed through :

- Form 3 : Pemeriksaan nyeri awal pasien
- Form 4 : Pemeriksaan indikator rasa nyeri non verbal
- Form 5 : Pemeriksaan rentang gerak
- Form 6 : Pemeriksaan kekuatan otot

By Principal Investigator or Sub Investigator on 1st Visit, 2nd Visit and 3rd Visit.

- Form 8 : thermal sensation, thermal comfort, and thermal acceptance and time of thermal sensation.

By Participant on 1st Visit, 2nd Visit and 3rd Visit.

- Adverse events symptoms, concomitant medication, rescue medication that will be described in the Diary Participant.

By Participant on Day 0 until study is completed.

